12.9. Publication Policy

- The results of this study may be published or presented at scientific meetings. If this is foreseen, the investigator agrees to submit all manuscripts or abstracts to the sponsor before submission. This allows the sponsor to protect proprietary information and to provide comments.
- The sponsor will comply with the requirements for publication of study results. In accordance with standard editorial and ethical practice, the sponsor will generally support publication of multisite studies only in their entirety and not as individual site data. In this case, a coordinating investigator will be designated by mutual agreement.
- Authorship will be determined by mutual agreement and in line with International Committee of Medical Journal Editors authorship requirements.

13. Statistical Considerations

Based on previous feasibility data, a sample size of 600 patients per arm (1:1 allocation, 1,200 total in both arms) would provide >99% Power to detect superiority for APC assuming a data loss of 15%. This same number of patients would also provide 90% Power to detect superiority for ADR, based on the expected ADR of 35% in the control arm, and 45% for the intervention arm. Based on the assumption that PPA will be at least 70% in both arms, Power for the PPA non-inferiority comparison will be > 90%.

The co-primary endpoint of PPA will be tested for non-inferiority using a non-inferiority margin of 10%. PPA will be calculated for each arm as the number of positive biopsies of total removed lesions. A resampling distribution of the difference in PPA will be used to calculate a two-sided 95% confidence interval for the difference: PPA(intervention)-PPA(control). Non-inferiority will be concluded if the lower confidence limit of the 95% two-sided confidence interval is above -10%. For APC, superiority will be assessed based on a one-sided test of the difference in mean rates at a 0.025 level of significance. For ADR, superiority will be assessed using a stratified CMH test at a one-sided 0.025 level of significance.

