Interim analysis: When approximately 600 subjects have completed the trial, an interim analysis will be conducted, and a conditional power analysis will be performed. The conditional power will assess the probability (power) that the study will meet its objectives on the superiority endpoint of APC and ADR, and on the non-inferiority of the PPA endpoint. If the conditional power is below 90% for either one of the co-primary endpoints or for ADR, an increase in the sample size from 1200 up to 2400 will be considered.

CPR, Protocol, Gastroenterology Artificial INtelligence System for detecting colorectal polyps (The GAIN Study) Document Number:

The increase in the sample size will be based on the probability of achieving success on both co-primary endpoints (APC and PPA) and success on the ADR endpoint. If the increase in sample size leads to an increase in the power for these endpoints to approximately 90%, then the study will enroll the additional subjects to allow the increase in power. Otherwise, the study may continue to the originally planned sample size of 1200 or stopped for futility. Due to a possible increase in the sample size, the final analysis will be done using a simple combination test, by transforming the test statistics of the interim patients, and the test statistic of the post-interim patients to standard normal (Z) statistics. Using prespecified weights of w1 = 1/2 and w2 = 1/2, the final Z = $\sqrt{w1}$ * interim Z + $\sqrt{w2}$ * post-interim Z. The interim analysis will be conducted by an independent statistician. Recommendations will be communicated confidentially to a select committee within Verily not directly involved in the study. Communication processes will be laid out in the interim analysis section of the statistical analysis plan.

The co-primary endpoints of APC and PPA will be analyzed using the ITT population. Sensitivity analyses will be conducted to assess the effect of missing complete or partial data by considering various imputation methods and will be described in the Statistical Analysis Plan. Subgroup analysis will include assessments of APC, ADR and PPA in groups defined by age-group, sex, race, ethnicity, site, colonoscopist and country

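### Does the 95% confidence-interval rule for PPA conflict with the combination test that section 13 prescribes for the final analysis?

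*Combined protocol and SAP*

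**What the plan says.** Section 13 first gives one base procedure per endpoint. For PPA, "PPA will be calculated for each arm as the number of positive biopsies of total removed lesions", and then "A resampling distribution of the difference in PPA will be used to calculate a two-sided 95% confidence interval for the difference". The decision is that "Non-inferiority will be concluded if the lower confidence limit of the 95% two-sided confidence interval is above -10" per cent; section 5.3 states the same comparison and calls it a statistical test of the null hypothesis. In the same paragraph APC gets a one-sided test of the difference in mean rates and ADR a stratified CMH test, each at one-sided 0.025. All three are worded for a single-stage analysis.

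The interim paragraph of section 13 follows. After about 600 subjects, the sample size may rise from 1,200 to at most 2,400 if conditional power for APC, PPA or ADR is below 90% and the increase would bring it to about 90%. Then: "Due to a possible increase in the sample size, the final analysis will be done using a simple combination test", carried out "by transforming the test statistics of the interim patients, and the test statistic of the post-interim patients to standard normal (Z) statistics". The weights are fixed in advance at one half per stage, and the combined statistic is the sum of the stage Z values, each multiplied by the square root of its weight. No endpoint is excluded.

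A separate SAP is to hold the unblinding and communication plan (12.5 and 13), the imputation methods and the population definitions (13). It is not part of the text reviewed here.

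**The concern.** PPA is co-primary, and its only stated procedure yields an interval, not a Z. Nothing says how each stage's PPA result becomes a Z against -10%, which interval matches the combined test, or which rule prevails if they differ. The two rules are not equivalent after an increase: an interval on all lesions weights the stages by size, while the combination test fixes equal weights. A trial could pass one and fail the other, and choosing between them after unblinding would be a post-hoc choice on a co-primary endpoint. The unit to be resampled is also unnamed, although lesions cluster within patients.

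**Working it through.** **1. The plan's own figure.** Section 13 claims more than 90% power for PPA at 70% in both arms with a 10-point margin. Lesions per arm for 90% power: (1.96 + 1.2816)² × 2 × 0.70 × 0.30 / 0.10² = 442 after rounding up. With 510 patients per arm (600 less the 15% loss that section 13 states for APC) and an assumed one independent lesion each, power is 93.6%. The claim is consistent, but the plan gives neither lesion counts nor clustering, so it cannot be reproduced exactly.

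**2. The two rules.** Let D_k be the PPA difference in stage k, SE_k its standard error, and Z_k = (D_k + 0.10)/SE_k.
- Combination: (Z1 + Z2)/√2 > 1.96. The weights are fixed and sum to 1, so one-sided error is 2.5% whatever the second-stage size.
- All lesions together: √(n1/N)·Z1 + √(n2/N)·Z2 > 1.96.

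At N = 1,200 (600 + 600) these are the same to first order. In a lesion-level model with assumed values they disagreed in 0.2% to 1.8% of trials, from variation in stage-wise standard errors alone.

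**3. Where they part at N = 2,400 (600 + 1,800).** The combination test needs Z2 > 2.772 - Z1. The all-lesions interval needs Z2 > (1.96 - 0.5·Z1)/0.866 = 2.263 - 0.577·Z1. These cross at Z1 = (2.772 - 2.263)/(1 - 0.577) = 1.20. Above that the interval is the harder test; below it, the easier.

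**4. Which interim results lead to an increase.** The plan does not say which effect conditional power assumes, so take both, for a PPA trigger alone.
- Observed trend: 2·Z1 - 2.772 < 1.2816 gives Z1 < 2.03; (1 + √3)·Z1 - 2.772 ≥ 1.2816 gives Z1 ≥ 1.48. The zone 1.48 to 2.03 lies wholly above 1.20, so the interval is conservative.
- Design effect (assuming exactly 90% power, so the true effect is 3.24 standard errors above the margin at N = 1,200): the zone is 0.08 to 1.76, on both sides of 1.20.

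**5. An example of conflict.** Z1 = 1.6, Z2 = 1.2. Combination: 2.8/1.414 = 1.98, pass. All lesions: 0.5 × 1.6 + 0.866 × 1.2 = 1.84, fail. With SE = 10/3.24 = 3.09 points at N = 1,200, the lower limits are -9.95% (inverting the combination test) and -10.3% (all lesions). Observed-trend conditional power at Z1 = 1.6 goes from 67% to 95%, so the plan's rule would enlarge this trial on PPA. The reverse also occurs: D1 = -8.0 and D2 = -5.5 points, with an assumed 300 then 900 independent lesions per arm and 70% control PPA, give an all-lesions limit of -9.88% (pass) and a combination Z of 1.81 (fail).

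**6. How often.** Stage-Z simulation, 4,000,000 draws per case, PPA trigger only. Drift is the true effect above the margin, in standard errors at N = 1,200; drift 1.5 means 32% power there, drift 3.24 means 90%.

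| Conditional power | N if raised | All-lesions one-sided error | Disagree, drift 1.5 | Disagree, drift 3.24 |
|---|---|---|---|---|
| Observed trend | 2,400 | 2.30% | 1.17% | 0.03% |
| Observed trend | smallest sufficient | 2.40% | 0.61% | 0.09% |
| Design effect | 2,400 | 2.74% | 3.99% | 0.17% |
| Design effect | smallest sufficient | 2.81% | 2.81% | 0.31% |

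These disagreement rates are not upper bounds. Adding an independent ADR trigger with 90% power and a jump to 2,400 gave all-lesions error of 2.3% (observed trend) and 2.6% (design effect), with 4.5% disagreement at drift 1.5 for the design effect. A lesion-level model with assumed values and a jump to 2,400 gave all-lesions error of 2.42% and 2.84%, and disagreement of 2.5% and 4.6% at a true difference of -5 points. Choosing N between 1,200 and 2,400 in the least favourable way, which the plan's rule does not do, gives 3.1%.

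**The case for a change.** The best case for a change is that the procedure cannot be run for PPA exactly as written, since a resampling interval is not a Z. The matters deferred to the SAP do not include this one. Disagreements also concentrate where they matter: among enlarged trials at drift 1.5, about 7% split. A clarifying sentence would cost almost nothing.

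The omission is real, but it does not leave two competing rules. The section 13 rules for APC and ADR are just as single-stage in wording, and no one would read them as overriding the combination test; PPA stands in the same position. A resampling distribution for each stage supplies either a standard error, hence Z_k, or a one-sided p-value with an inverse-normal transform. Both fit the text.

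The resampling unit is a separate matter. Under assumed values (1.2 to 2.0 lesions per patient, intra-patient correlation 0.1 to 0.3), resampling lesions gives one-sided error of 4.1% to 10.8%, and resampling patients 2.5% to 2.6%. None of those inputs is in the documents. Subjects are randomized (7.2.3) and section 13 splits the stages by patients, so the patient is the unit a competent analyst would resample. These figures do not bear on the combination rule.

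**Conclusion.** No change to the plan follows. The combination test is the final analysis for every endpoint it covers, PPA included, and it holds one-sided error at 2.5%. The stage-wise Z, the matching interval and the resampling unit are unwritten details with ordinary answers. If someone instead decided on the all-lesions interval, the error would be about 2.3% to 2.8% under the plan's rule. The verdict would differ in 0.03% to 0.31% of trials at 90% planned power, and in roughly 1% to 4% where the true effect is only 1.5 standard errors above the margin. These sizes rest on a normal approximation, a PPA-only trigger, and conditional power taken either at the observed trend or at a design effect with 90% power. With no increase in sample size, the two rules agree to first order.

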Adverse Event	AE	Any untoward medical occurrence, unintended disease or injury in subjects, users or other persons, that is considered a change from baseline or pre-study status, whether or not related to the investigational medical device.
Case Report Form	CRF	A set of documents, designed for complete recording of all relevant subject and device related data, as required by the clinical investigation plan.
Trial Master File	TMF	Contains essential documents for a clinical trial that may be subject to regulatory agency oversight.
Clinical Investigation	N/A	Any controlled systematic study in human subjects, undertaken to verify the safety and performance of a specific medical device, under normal conditions of use. This is also known as a Clinical Study or Clinical Trial.
Clinical Research Associate	CRA	A person appointed by the sponsor and responsible for monitoring and reporting on the progress of the clinical investigation. This is also known as a Monitor.
Contract Research Organization	CRO	Contract research organizations are independent contractors who assume, by contract, some or all of the regulatory responsibilities of a sponsor and/or monitor.
Informed Consent	IC	A process by which a subject voluntarily confirms his or her willingness to participate in a particular trial, after having been informed of all aspects that are relevant to the subject's decision, including potential risks and benefits to participate. Informed consent is documented by means of a written, signed, and dated informed consent form. Informed consent continues throughout the trial.
Intent to treat	ITT	All randomized subjects.
Investigational Device	N/A	Any medical device intended for use by an appropriately qualified practitioner when conducting clinical investigations in an adequate clinical environment.
Modified Intent to treat	mITT	The subset of ITT subjects, including only those indicated for Screening or Surveillance
Per Protocol	PP	The subset of ITT subjects, excluding those whose procedure could not be completed per protocol (e.g. poor bowel prep).
Principal Investigator	PI	The investigator responsible for the conduct of a clinical investigation and who takes the clinical responsibility for the well being of the subjects involved.
Serious Adverse Event	SAE	A Serious Adverse Event (also referred to as Adverse Incident) is defined as an adverse event that is anticipated or unanticipated and that reasonably suggests that one of the manufacturers devices has or may have caused or contributed to a death or serious injury. A Serious Adverse Event is an Adverse Event that led to: (a) death, (b) serious deterioration

VerilyCPR, Protocol, Gastroenterology Artificial INtelligence System for detecting colorectal polyps (The GAIN Study)
Document Number:

		in the health of the subject that either resulted in a (i) life-threatening illness or injury or (ii) permanent impairment of a body structure or a body function, or (iii) in-patient or prolonged hospitalization or (iv) medical or surgical intervention to prevent life-threatening illness or injury or permanent impairment to a body structure or a body function or (c) fetal distress, fetal death or a congenital abnormality or birth defect. These events are typically reportable to health authorities.
Sponsor	N/A	An individual or an organization which takes responsibility for the initiation and/or implementation of a clinical investigation.
Sub-Investigator	Sub-I	A member of the clinical study team with appropriate credentials and is supervised by the Principal Investigator at a site and allowed to perform critical trial-related procedures and/or to make key trial-related decisions.
Subject/ Research Subject	N/A	A human being, either a patient or a non-patient volunteer, participating in a clinical investigation.
Unanticipated Adverse Device Effect	UADE	Serious adverse effect on health or safety or any life-threatening problem or death caused by, or associated with, a device, if that effect or problem was not previously identified in nature, severity, or degree of incidence in the investigational plan or application (including a supplementary plan or application), or any other unanticipated serious problem associated with a device that relates to the rights, safety, or welfare of subjects.
